7.2 Key Secondary Efficacy Analyses

The key secondary endpoints will be estimated based on the FAS, defined as in Section 5.4.1.

Together with the primary endpoint and the key secondary endpoints, this family of tests will be conducted hierarchically to maintain a familywise Type I error rate of 4.98%. Each test within this family will be conducted at the 4.98% level if the preceding test was significant at the 4.98% level.

7.2.1 Proportion of Eyes Developing Any Sight-Threatening Complication

The first key secondary efficacy endpoint of interest is the proportion of eyes developing any of the following from baseline through Week 48:

- PDR or ASNV;
- Vitreous hemorrhage or tractional retinal detachment believed to be due to PDR; or
- DME.

The development of the above sight-threatening complications is tabulated from adverse events, procedures and eCRFs.

The following intercurrent events will be evaluated in this key secondary endpoint:

- Treatment misallocation at 1 or more study visits.

- Use of prohibited medications in the study eye.

-Premature discontinuation from study treatment due to study eye adverse events or due to lack of efficacy.

-Premature discontinuation from study treatment due to events unrelated to study treatment such as malignancies, systemic infections, trauma, or other systemic adverse events that are not treatment-related, including discontinuations due to COVID-19.

The same analysis method from the primary efficacy endpoint will be used for the first key secondary efficacy endpoint. See Section 7.1.2.

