7.1.1.4 Intercurrent Events

The following intercurrent events (ICEs) may impact the assessment of the primary efficacy endpoint:

- 1. Treatment misallocation at 1 or more study visits.
- 2. Use of prohibited medications in the study eye.
- 3. Development of sight-threatening complication(s) and initiation of open-label KSI-301 5 mg treatment, panretinal photocoagulation, or other treatment for DME, ASNV, and/or PDR.
- 4. Premature discontinuation from study treatment due to study eye adverse events or due to lack of efficacy.
- 5. Premature discontinuation from study treatment due to events unrelated to study treatment such as malignancies, systemic infections, trauma, or other systemic adverse events that are not treatment-related, including discontinuations due to COVID-19.

Intercurrent events will be classified by the Sponsor prior to treatment code unmasking to prevent potential bias. Intercurrent events and the time to intercurrent events will be tabulated and listed by treatment group. Strategies for addressing the potential impact of these intercurrent events are described below.

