7.1.2 Analysis of Primary Efficacy Endpoint

The primary efficacy endpoint will be estimated based on the FAS, i.e., all randomized subjects who received at least one treatment injection and have gradable DRSS value at baseline.

The statistical analysis will be performed using the Cochran-Mantel-Haenszel (CMH) method,

A 'Hypothetical' strategy will be applied for all intercurrent events where measurements after occurrence of intercurrent event will be imputed using the last observation carry forward (LOCF) procedure. For patients who develop sight-threatening complication(s) and have non-gradable value at their first visit where open-label treatment is administered, the non-gradable values will be imputed as no change from baseline. For patients without intercurrent event, missing and non-gradable values at Week 48 will be imputed using LOCF. Baseline will be carried forward if all post-baseline observations are missing or non-gradable. Non-gradable values are observations where DRSS level is 90.

The p-value will be reported for comparison between KSI-301 and sham groups. In addition, the weighted percentages difference between the KSI-301 and sham (i.e., KSI-301 – sham) and 95.02% CI of the difference will be presented. Percentages are calculated as 100×number of "responders"/number of patients in FAS. Weighted percentages are based on weighted average of observed estimates across strata using CMH weights. The CI are based on the normal approximation to the binomial proportions.

The CMH method as described for the primary efficacy analysis will be used for all sensitivity analyses below.

7.1.3 Sensitivity Analysis 1

In this analysis, a 'Composite' strategy will be applied for all intercurrent events where patients with occurrence of intercurrent event by Week 48 will be considered as non-responders. For patients without intercurrent event, missing and non-gradable values at Week 48 will be imputed using LOCF, and baseline will be carried forward if all post-baseline observations are missing or non-gradable as in the primary analysis.

7.1.4 Sensitivity Analysis 2

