This analysis will follow the same 'Hypothetical' strategy for handling of intercurrent events and analysis method as the primary analysis, with the exception that patients with the following significant protocol deviations will be excluded from the analysis: deviation from key inclusion/exclusion criteria as defined in Section 7.1.1.1, treatment misallocation at 1 or more study visits by Week 48, and use of prohibited medications in study eye at any point by Week 48.

7.1.5 Sensitivity Analysis 3

This analysis will follow the same 'Hypothetical' strategy for handling of intercurrent events and analysis method as the primary analysis, with the exception that patients with baseline DRSS level outside of levels 47 and 53 will be excluded from the analysis.

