7.2.2 Proportion of Eyes Improving ≥3 Steps on DRSS

The second key secondary efficacy endpoint of interest is proportion of eyes improving ≥ 3 steps on DRSS from baseline at Week 48. The same intercurrent events and analysis method from the primary efficacy endpoint will be used. See Sections 7.1.1.4 and 7.1.2.

A sensitivity analysis for this key secondary efficacy endpoint will be performed where patients with baseline DRSS level outside of levels 47 and 53 will be excluded from the analysis.

7.2.3 **Proportion of Eyes Developing PDR**

The third key secondary efficacy endpoint of interest is the proportion of eyes developing PDR from baseline through Week 48. The same intercurrent events and analysis method from the first key secondary efficacy endpoint will be used. See Section 7.2.1.

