7.3 Additional Secondary Efficacy Analyses

As specified in Section 4.0, the Primary Analysis will evaluate the efficacy of KSI-301 compared to sham from Day 1 up to Week 48.

Table 4 lists the additional secondary efficacy endpoints, efficacy variable derivations, reporting statistics and analysis methods for the Primary Analysis and until the end of study.

Binary secondary efficacy endpoints will utilize the Cochran-Mantel-Haenszel (CMH) method stratified by the randomization stratification factors (i.e. baseline DRSS level and HbA1c level).

Time to event endpoints will be analyzed using the Kaplan-Meier estimates. The number of observations censored will be provided for each treatment group. The 50th percentile of Kaplan-Meier estimates will be used to estimate the median time to first event in each treatment group. A 2-sided 95% CI will be provided for the estimates. A log-rank test stratified by the randomization stratification factors (i.e. baseline DRSS level and HbA1c level) will be performed to compare the survival distributions between the treatments. The hazard ratio and its 95% CI will be reported from a Cox regression model stratified by the same randomization stratification factors with treatment as the covariate. For patients not known to have had an event at the time of the analysis data cutoff, the time will be censored at the date of the last scheduled study visit at analysis data cutoff.

Continuous endpoints (e.g. mean change from baseline in BCVA) will utilize a Mixed Model for Repeated Measures (MMRM). The model assumes missing at random (MAR). The model will include the change from baseline value as the dependent variable; categorical covariates of treatment group, protocol scheduled visit, treatment × visit interaction, and the randomization stratification factors (i.e. baseline DRSS level and HbA1c level) as well as continuous covariate of baseline BCVA, as fixed effects; and then subject as a random effect. Within-subject correlations will be assumed to follow an unstructured covariance matrix. If the model assuming an unstructured covariance matrix does not converge, a heterogeneous compound symmetry structure or an AR(1) covariance structure will be fitted.

For all additional secondary efficacy endpoints, data after the occurrence of intercurrent event will be censored, and missing and non-gradable data will not be imputed. Only observed, gradable and non-censored data will be used for analysis.

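### The SAP gives no intercurrent-event strategy of its own for the two complication endpoints, and the LOCF rule it points to would count a complication seen after such an event as no complication

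*SAP*

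**What the plan says.** SAP 7.2.1 defines the first key secondary endpoint as the proportion of eyes developing PDR or ASNV, vitreous hemorrhage or tractional detachment due to PDR, or DME by Week 48. Events are taken from adverse events, procedures and eCRFs. It then says "The following intercurrent events will be evaluated in this key secondary endpoint" and lists four: treatment misallocation, prohibited medication in the study eye, stopping treatment for a study-eye adverse event or lack of efficacy, and stopping for reasons unrelated to treatment. For the analysis it says "The same analysis method from the primary efficacy endpoint will be used for the first key secondary efficacy endpoint" and points to 7.1.2. For PDR alone, 7.2.3 says "The same intercurrent events and analysis method from the first key secondary efficacy endpoint will be used".

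Section 7.1.2 was written for DRSS. It applies a hypothetical strategy to all intercurrent events, under which "measurements after occurrence of intercurrent event will be imputed using the last observation carry forward (LOCF) procedure", and it uses all FAS patients as the denominator.

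The key secondary tests are hierarchical: "Each test within this family will be conducted at the 4.98% level if the preceding test was significant at the 4.98% level". The sensitivity analyses in 7.1.3 to 7.1.5 are for the primary endpoint. Section 7.2.2 has one of its own; 7.2.1 and 7.2.3 have none.

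**The concern.** DRSS is graded visit by visit, so carrying a value forward at least has a meaning. A complication is a cumulative event: once it has occurred by Week 48, the eye has had it. Eyes enter at DRSS 47 or 53, and ASNV, vitreous hemorrhage, tractional detachment and center-involved DME are exclusions. The status before a listed event is therefore 'no complication' unless one has already occurred. Carrying that status forward overwrites a complication recorded later, and gives an eye lost from follow-up zero further risk. This estimates neither what would have happened without the intercurrent event (hypothetical) nor what did happen regardless of it (treatment policy).

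Such complications can be observed, because Protocol 7.1 encourages participants who stop treatment to keep attending. Two of the listed events may also be linked to a developing complication: stopping for lack of efficacy, and prohibited study-eye medication, which under Protocol 6.8.2 includes non-study anti-VEGF drugs and steroids.

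The result would then depend partly on which arm has more listed events and on which reading is programmed. Because 7.2.1 is the first key secondary test, its failure would block the two tests after it.

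**Working it through.** **Two readings of the reference to 7.1.2**

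- Reading A (literal): the LOCF rule and FAS denominator apply. A first complication after a listed event becomes 'no complication'.
- Reading B (CMH test only): SAP 7.1.4 names two things separately, the "strategy for handling of intercurrent events and analysis method as the primary analysis", so 'analysis method' could mean the test alone. Nothing observed is overwritten, but the four events have no strategy.

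Under both readings, complications before a listed event, or observed after stopping for an unlisted reason, are counted.

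**Inputs.** From the SAP: about 120 per arm (Section 9.0) and two-sided alpha 0.0498 (7.1.1.3, 7.2). The plan states no complication rate or power for these endpoints, so there is no figure to reproduce. Assumed: 48-week risk *r* with a constant hazard; share *d* of eyes with a listed event at week *t* (base case 20); share *f* of those eyes still followed (0.5 where used).

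**Formula.** Unconditional risk between week *t* and Week 48: L = (1−r)^(t/48) − (1−r). Risk as analysed under reading A: r − d·L. Of the lost events, a share *f* is observed and overwritten and 1−f is unobserved. Benefit is sham risk minus KSI-301 risk.

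**No true effect, 25% risk in both arms, t = 20**

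- L = 0.75^(20/48) − 0.75 = 0.8870 − 0.75 = 0.1370.
- KSI-301, d = 15%: 25 − 0.15 × 13.70 = 22.94%, or 2.5 events lost per 120.
- Sham, d = 5%: 25 − 0.05 × 13.70 = 24.31%, or 0.8 events lost per 120.
- False benefit: 24.31 − 22.94 = 1.4 points. With f = 0.5, 0.7 is overwritten and 0.7 is unobserved dropout risk.
- With 10% versus 5%: 0.05 × 13.70 = 0.7 points, of which 0.3 is overwritten.

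**Range with no true effect** (risk 10 to 35%, event at Week 8 to 32, 10% or 15% versus 5%)

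- Smallest: r = 10%, t = 32, 10% versus 5%: 0.05 × 3.22 = 0.16 points.
- Largest: r = 35%, t = 8, 15% versus 5%: 0.10 × 28.07 = 2.81 points.
- Rejection rate (normal approximation): 5.0% to 7.5%, against 4.98%.
- Reversing the imbalance gives the same size as apparent harm. Equal shares give zero.

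**True effect, t = 20, reading A**

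| True risk, KSI-301 v sham | Listed events, KSI-301 v sham | True difference | Analysed difference | Power, true to analysed |
|---|---|---|---|---|
| 10% v 25% | 10% v 10% | 15.0 | 14.2 | 88% to 85% |
| 10% v 25% | 5% v 15% | 15.0 | 13.2 | 88% to 80% |
| 10% v 25% | 15% v 5% | 15.0 | 15.2 | not reduced |
| 5% v 15% (PDR alone) | 10% v 10% | 10.0 | 9.4 | – |
| 5% v 15% (PDR alone) | 5% v 15% | 10.0 | 8.9 | – |
| 5% v 15% (PDR alone) | 15% v 5% | 10.0 | 10.0 | – |

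**Hazard changing after the listed event** (10% v 25%)

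- KSI-301 eyes take the sham hazard, shares 15% v 5%: hypothetical target 15.0, treatment policy 13.6, analysed 15.2.
- Eyes with a listed event have twice the hazard, shares 5% v 15%: true 16.5, analysed 13.2.

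**Simulation check** (stratified CMH, four equal strata, 12,000 trials, f = 0.5, t = 20)

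| Scenario (listed events, KSI-301 v sham) | Quantity | Full follow-up | Reading A | Observed events counted |
|---|---|---|---|---|
| Null, 15% v 5% | Mean difference | 0.0 | 1.4 | 0.7 |
| Null, 15% v 5% | Rejection | 4.9% | 5.6% | 5.1% |
| Null, 10% v 5% | Mean difference | 0.0 | 0.7 | 0.4 |
| Null, 10% v 5% | Rejection | 4.9% | 5.2% | 5.1% |
| 10% v 25% risk, 5% v 15% | Mean difference | 15.0 | 13.2 | 14.1 |
| 10% v 25% risk, 5% v 15% | Power | 87% | 80% | 84% |

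Kaplan-Meier gave 0.0, 0.0 and 15.0 in the three scenarios, with non-informative loss. The Monte Carlo standard error of the null rejection rates is about 0.2 percentage points.

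**Do other planned analyses cover the gap?** The 7.3 Kaplan-Meier, log-rank and Cox analyses partly check the dropout half. But for those endpoints "data after the occurrence of intercurrent event will be censored, and missing and non-gradable data will not be imputed", so they also leave out complications after an intercurrent event. They report a median and a hazard ratio rather than a Week 48 risk difference, and none is for PDR alone. Section 7.1.1.4 says "Intercurrent events and the time to intercurrent events will be tabulated and listed by treatment group", and later adverse events are listed. That allows a hand count, but no planned treatment effect includes these complications.

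**The case against.** The strongest reply is that reading A is strained. The LOCF text in 7.1.2 speaks of measurements and ungradable DRSS values, while 7.2.1 counts events from adverse-event, procedure and eCRF records, where no Week 48 measurement exists to overwrite. On reading B nothing observed is lost, and the defect is one of drafting. This has force, but it does not settle the text: the rule in 7.1.2 covers all intercurrent events, the event list in 7.2.1 was adapted to this endpoint by dropping the complication event itself, and the handling was not adapted. If reading B is meant, the four events still have no strategy.

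Second, about half of the quoted bias is unobserved dropout risk rather than overwriting, and that half follows the LOCF rule in Protocol 9.4.3. This stands with half of the eyes followed; counting observed events restores simulated power only from 80% to 84%. It is why a second sensitivity analysis is needed.

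Third, the effect is small. The 7.5% rejection rate needs 35% risk, events at Week 8 and a threefold imbalance. At 10% versus 5%, simulated rejection is close to nominal. These are also rates for a single test that is reached only after earlier successes, not familywise error rates. All of this stands.

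Fourth, an eye that develops DME, PDR or ASNV switches to open-label treatment at the diagnosis visit, so most complications should be recorded before any stop or prohibited drug. That limits the number at risk of being overwritten. The doubled-hazard case is an assumption without support in the documents.

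Finally, a hypothetical estimand is a legitimate choice. It is, but carrying 'no event' forward does not estimate one.

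**Conclusion.** The concern holds. SAP 7.2.1 and 7.2.3 either inherit a rule that miscounts a cumulative event or leave the handling of their listed intercurrent events unstated. No sensitivity analysis or 7.3 analysis supplies the missing treatment effect. The bias is probably small and can go either way: 0.2 to 2.8 points with no true effect over the assumed ranges, zero with equal shares of listed events, and a 15.0-point effect analysed as 13.2 to 15.2. These figures assume reading A, 120 per arm, a constant hazard and event shares that the documents do not give. With half of the affected eyes still followed, reading B removes about half of the bias. The point should be fixed because it touches two of the three alpha-controlled key secondary tests and the correction is cheap. Confidence is medium, mainly because the intended reading is uncertain.

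**What to change.** 1. In SAP 7.2.1 and 7.2.3, state that every qualifying complication (or PDR) observed through Week 48 counts as an event regardless of the listed intercurrent events. If the hypothetical estimand is kept for the main test, say so in those sections and add this count as a pre-specified sensitivity analysis.
2. For both endpoints, add a Week 48 Kaplan-Meier risk difference, stratified by the randomization factors, as a sensitivity analysis for eyes not followed to Week 48. Censor at loss to follow-up, not at the intercurrent event.

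Reusing the composite rule of 7.1.3 would not help, because 'non-responder' is undefined for a harmful event. Censoring of DRSS after a sight-threatening complication is unaffected.

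The cost is one sentence in each section and two to four extra outputs from data already collected. The estimates may be slightly less favourable. The Kaplan-Meier result assumes non-informative loss, so it should remain a sensitivity analysis.

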7.2.2 Proportion of Eyes Improving ≥3 Steps on DRSS

The second key secondary efficacy endpoint of interest is proportion of eyes improving ≥ 3 steps on DRSS from baseline at Week 48. The same intercurrent events and analysis method from the primary efficacy endpoint will be used. See Sections 7.1.1.4 and 7.1.2.

A sensitivity analysis for this key secondary efficacy endpoint will be performed where patients with baseline DRSS level outside of levels 47 and 53 will be excluded from the analysis.

7.2.3 **Proportion of Eyes Developing PDR**

The third key secondary efficacy endpoint of interest is the proportion of eyes developing PDR from baseline through Week 48. The same intercurrent events and analysis method from the first key secondary efficacy endpoint will be used. See Section 7.2.1.

7.3 Additional Secondary Efficacy Analyses

As specified in Section 4.0, the Primary Analysis will evaluate the efficacy of KSI-301 compared to sham from Day 1 up to Week 48.

Table 4 lists the additional secondary efficacy endpoints, efficacy variable derivations, reporting statistics and analysis methods for the Primary Analysis and until the end of study.

Binary secondary efficacy endpoints will utilize the Cochran-Mantel-Haenszel (CMH) method stratified by the randomization stratification factors (i.e. baseline DRSS level and HbA1c level).

Time to event endpoints will be analyzed using the Kaplan-Meier estimates. The number of observations censored will be provided for each treatment group. The 50th percentile of Kaplan-Meier estimates will be used to estimate the median time to first event in each treatment group. A 2-sided 95% CI will be provided for the estimates. A log-rank test stratified by the randomization stratification factors (i.e. baseline DRSS level and HbA1c level) will be performed to compare the survival distributions between the treatments. The hazard ratio and its 95% CI will be reported from a Cox regression model stratified by the same randomization stratification factors with treatment as the covariate. For patients not known to have had an event at the time of the analysis data cutoff, the time will be censored at the date of the last scheduled study visit at analysis data cutoff.

Continuous endpoints (e.g. mean change from baseline in BCVA) will utilize a Mixed Model for Repeated Measures (MMRM). The model assumes missing at random (MAR). The model will include the change from baseline value as the dependent variable; categorical covariates of treatment group, protocol scheduled visit, treatment × visit interaction, and the randomization stratification factors (i.e. baseline DRSS level and HbA1c level) as well as continuous covariate of baseline BCVA, as fixed effects; and then subject as a random effect. Within-subject correlations will be assumed to follow an unstructured covariance matrix. If the model assuming an unstructured covariance matrix does not converge, a heterogeneous compound symmetry structure or an AR(1) covariance structure will be fitted.

For all additional secondary efficacy endpoints, data after the occurrence of intercurrent event will be censored, and missing and non-gradable data will not be imputed. Only observed, gradable and non-censored data will be used for analysis.

Additional Secondary Efficacy Endpoint	Variable Derivation [Source]	Summary Statistics [Analysis Set]	Method of Analysis		
Proportion of eyes developing PDR or ASNV from baseline through Week 48	Binary endpoint: patients developed PDR or ASNV (yes/no) [Sight-threatening Complication/EDC]				
Proportion of eyes developing vitreous hemorrhage or tractional retinal detachment, believed to be due to PDR, from baseline through Week 48	Binary endpoint: patients developed vitreous hemorrhage or tractional retinal detachment believed to be due to PDR (yes/no) [Sight-threatening Complication/EDC/Review of AEs]				
Proportion of eyes developing DME from baseline through Week 48	Binary endpoint: patients developed DME (yes/no) [Sight-threatening Complication/EDC]	Difference in proportions (%) and 95% CI at each time point [FAS], up to Week 48	CMH method adjusting for randomization stratification factors (similar to Section 7.1.2)		
Proportion of eyes with a ≥ 2 - step or a ≥ 3 -step worsening on DRSS from baseline at Week 48	Binary endpoints: patients with a ≥2-step worsening in DRSS (yes/no); patients with a ≥3-step worsening in DRSS (yes/no);				
Proportion of eyes who lose ≥ 5 , ≥ 10 , or ≥ 15 letters in BCVA from baseline by visit over time	Binary endpoints: patients had a BCVA loss \geq 5 (yes/no); patients had a BCVA loss \geq 10 (yes/no); patients had a BCVA loss \geq 15 (yes/no). [Visual Acuity Score/EDC]				
Time to first development of PDR, ASNV, or DME through Week 48	Time to event endpoint: Time from first treatment to development of PDR, ASNV, or DME (in months) [Sight-threatening Complication/EDC]				

Table 4: Additional Secondary Efficacy Endpoints and Analysis Methods

KS301P106 SAP Version 0.1 KSI-301 – Kodiak Sciences Inc.

Additional Secondary Efficacy Endpoint	Variable Derivation [Source]	Summary Statistics [Analysis Set]	Method of Analysis			
Time to first development of PDR or ASNV through Week 48Time to event endpoint: Time from first treatment to development of PDR or ASNV (in months) [Sight-threatening Complication/EDC]						
Time to first development of vitreous hemorrhage or tractional retinal detachment, believed to be due to PDR through Week 48	to first development of us hemorrhage or onal retinal detachment, red to be due to PDR gh Week 48		Kaplan-Meier and Cox regression model stratified by randomization stratification factors (Section 7.3)			
of AEs] Time to first development of DME through Week 48 Time from first treatment to development of DME (in months) [Sight-threatening Complication/EDC]						
Mean change in SD-OCT central subfield thickness (CST) from baseline by visit over time	Continuous Endpoint: Change from baseline to each time point	LS Mean difference in change from baseline to each time point and 95% CI [FAS], up to Week 48 [FAS], up to end of study	MMRM (Section 7.3) adjusting for baseline CST, with time, treatment, and time*treatment interaction and randomization stratification as factors Unstructured covariance matrix			
Mean change in BCVA from baseline by visit over time	Continuous Endpoint: Change from baseline to each time point [Visual Acuity Score/EDC]	LS Mean difference in change from baseline to each time point and 95% CI [FAS], up to Week 48 [FAS], up to end of study	MMRM (Section 7.3) adjusting for baseline BCVA, with time, treatment, and time*treatment interaction and randomization stratification as factors Unstructured covariance matrix			

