5.2.1 Ocular Exclusion Criteria

Where applicable, ocular exclusion criteria will be determined by an independent, masked image reading center.

- 1. Presence of center-involved DME in the study eye, defined for this purpose as CST of \geq 320 microns on SD-OCT (Heidelberg Spectralis or equivalent value on other OCT instruments).
- 2. Prior PRP in the Study Eye.

- 3. Current anterior segment neovascularization (ASNV), vitreous hemorrhage, or tractional retinal detachment in the Study Eye.
- 4. Prior intravitreal anti-VEGF treatment in the Study Eye for DR or DME.
- 5. Prior intravitreal or periocular steroid in the Study Eye for DR or DME.
- 6. Prior use of an investigational intravitreal treatment for DR or DME in the Study Eye.
- 7. History of vitreoretinal surgery in the Study Eye
- 8. History of retinal detachment or treatment or surgery for retinal detachment in the Study Eye.
- 9. History of cataract surgery in the Study Eye within 2 months of screening.
- 10. History of YAG laser capsulotomy in the Study Eye within 2 months of screening.
- 11. Uncontrolled glaucoma (defined as intraocular pressure ≥25 mmHg despite treatment with antiglaucoma medication) in the Study Eye.
- 12. History of glaucoma-filtering surgery (trabeculectomy or tube shunt) in the Study Eye.
- 13. History of uveitis in either eye.
- 14. Significant media opacities, including cataract, in the Study Eye that might interfere with visual acuity, assessment of safety, OCT, or FP.
- 15. Cataract in the Study Eye that in the judgment of the Investigator is expected to require surgical extraction within 12 months of screening.
- 16. Aphakia in the Study Eye.
- 17. Active retinal disease other than the condition under investigation in the Study Eye.
- 18. Any history or evidence of a concurrent ocular condition present in the Study Eye, that in the opinion of the Investigator could require either medical or surgical intervention or alter visual acuity during the study (e.g., vitreomacular traction, epiretinal membrane).
- 19. Active or suspected ocular or periocular infection or inflammation in either eye at Day 1.
- 20. BCVA of hand motion or worse in the non-Study Eye or non-physical presence of a non-Study Eye (i.e., monocular).

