Other statistics (e.g., CIs) will be presented using the same general rules outlined above or assessed for the most appropriate presentation based on the underlying data.

Unless noted otherwise, statistical significance testing will be two-sided and performed using α =0.05. Confidence intervals (CIs) will be calculated at the 95% level, reflecting a type I error rate of 0.05. P-values will be reported for all statistical tests, rounded to four decimal places. P-values less than 0.0001 will be displayed as "<0.0001"; p-values greater than 0.9999 will be displayed as ">0.9999".

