9.0 SAMPLE SIZE CONSIDERATIONS

A sample size of approximately 240 participants with a target enrollment of approximately 120 participants in each treatment group (1:1 ratio) was calculated using the following assumptions:

- Anticipated of participants with a ≥2-step improvement from baseline in DRSS score in the KSI-301 5 mg Q24W group versus in the sham group.
- Statistical power of $\geq 90\%$.
- Overall Type I error rate of 0.05.
- The statistical method used to compare the proportion with a ≥2-step improvement from baseline in DRSS score for the KSI-301 treatment group at Week 48 compared with sham will be the Cochran-Manzel Haenszel (CMH) method,

• Lost to follow-up/dropout rate of approximately

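### The DME analyses omit baseline CST, a value the trial collects and the DME definition depends on; the cost is some efficiency, not validity

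*SAP*

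**What the plan says.** SAP 7.3 sets the methods for the additional secondary endpoints. Binary endpoints use CMH and time-to-event endpoints use a log-rank test, both "stratified by the randomization stratification factors (i.e. baseline DRSS level and HbA1c level". The hazard ratio comes from "a Cox regression model stratified by the same randomization stratification factors with treatment as the covariate". Table 4 applies these methods to the proportion with DME, time to DME, and time to first PDR, ASNV or DME, all through Week 48.

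Baseline CST is available. SoA-A schedules SD-OCT at Screening, SAP 5.3 takes the last pre-dose value as baseline, and SAP 6.2.1 summarizes CST by arm. It is a covariate in one analysis only, that of mean CST change: "MMRM (Section 7.3) adjusting for baseline CST".

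Two protocol passages tie CST to DME:

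- **Entry.** Section 5.2.1 excludes "Presence of center-involved DME in the study eye, defined for this purpose as CST of" 320 microns or more, so every eligible eye starts below 320.
- **Event.** Table 3 (Section 4.1.3.1) gives two routes to DME: CST of at least 320 microns with a loss of at least 5 letters from Day 1, or CST of at least 350 microns. In both, the investigator must attribute the finding to DME.

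Protocol 9.4.3 plans logistic models to supplement the tests of proportions but names no covariates. SAP 7.3 does not carry those models forward.

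**The concern.** Both routes to DME require CST to reach a fixed value, so an eye that enters at 315 microns is much nearer to an event than one that enters at 240. Within a DRSS-by-HbA1c stratum the plan treats the two alike. Chance differences between arms in starting CST then add noise to the DME comparison, and a baseline value already in the database could remove part of it.

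This matters because nothing in the plan shows that the DME comparisons have enough events. The sample size ("A sample size of approximately 240 participants with a target enrollment of approximately 120 participants in each treatment group (1:1 ratio") and the "Statistical power of" 90% or more both refer to the DRSS response at Week 48.

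**Working it through.** **1. The plan's own figure.** N = 240 can be neither reproduced nor refuted, because the response rates and dropout rate are redacted in the public copy. With 120 per arm, no dropout and two-sided alpha 0.05, power is 90% for response rates of 18.4% vs 5%, 26.0% vs 10%, 32.7% vs 15% or 39.0% vs 20%. No figure is stated for DME, so this point does not touch N.

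**2. Events needed for DME.** SAP 5.1 says that "statistical significance testing will be two-sided and performed using α =0.05". For 80% power with 1:1 allocation, Schoenfeld's formula is D = 4(z0.975 + z0.80)² / (ln HR)².
- HR 0.4: 4 × (1.960 + 0.842)² / 0.916² = 31.4 / 0.840 = 37.4, so 38 events.
- HR 0.5: 31.4 / 0.480 = 65.3, so 66 events.

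Assumed sham DME rates of 10% and 20% with HR 0.4 gave about 16 and 33 events in the simulation below. The DME analyses may well be short of events.

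**3. How strongly baseline CST predicts DME.** Assume baseline CST is normal with mean 270 or 285 and SD 25, truncated below 320; that the SD of the change is 20-60 microns; and that there is a 30% chance of a 5-letter loss. Applying both CST routes gives a log odds ratio of 0.64-1.92 per SD of baseline CST and an R² of 5-12%. The steepest slope (1.92) goes with the lowest incidence (4.5%), so strong prediction and many events tend not to occur together.

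**4. SAP analysis against adjusted analysis.** The simulation used 240 participants, DME detected at Weeks 8, 20, 32, 44 and 48, HR 0.4, baseline CST normal (270, SD 25) truncated below 320, 8% dropout, four non-prognostic strata and 1,200 replicates. The Monte Carlo SE of a power is about 1.4 points. All rates are assumptions.
- SAP risk difference: Σ wᵢ(pᵢ₁ − pᵢ₀), with the CMH weights of SAP Appendix 2.
- Adjusted risk difference: fit a logistic model with baseline CST, predict each participant's risk under KSI-301 and under sham, and average the differences.
- Variance ratio: (adjusted SD / CMH SD)².

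| Sham DME | log HR per SD of CST | Cox power %, SAP → with CST | SE of log HR, SAP → with CST | Variance ratio, risk difference |
|---|---|---|---|---|
| 10% | 0.4 | 35.8 → 35.7 | 0.599 → 0.601 | 1.00 |
| 10% | 0.7 | 34.6 → 35.3 | 0.595 → 0.599 | 0.99 |
| 10% | 1.0 | 35.9 → 38.1 | 0.594 → 0.601 | 0.94 |
| 10% | 1.4 | 32.9 → 37.9 | 0.584 → 0.597 | 0.90 |
| 20% | 0.4 | 67.0 → 67.7 | 0.396 → 0.398 | 0.97 |
| 20% | 0.7 | 66.6 → 68.3 | 0.396 → 0.398 | 0.96 |
| 20% | 1.0 | 60.9 → 66.2 | 0.390 → 0.395 | 0.87 |
| 20% | 1.4 | 57.5 → 69.3 | 0.377 → 0.386 | 0.79 |

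If CST is not prognostic, nothing is gained and nothing material is lost (20% sham: Cox power 70.8 → 70.7).

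**5. Where the Cox gain comes from.** In every row the SE of the log HR rises slightly. In the last row the mean log HR moves from −0.780 to −0.907 while the SE goes from 0.377 to 0.386, so estimate/SE goes from 2.07 to 2.35. The gain is a hazard ratio conditional on CST that lies further from 1. Only the risk difference becomes more precise.

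**6. Sensitivity to the spread of CST change.** A large-sample check assumed baseline mean 275 and SD 25, sham DME 12%, risk ratio 0.4 and a 30% chance of letter loss. The gain in effective sample size was 19%, 11%, 7% and 3.6% for a peak-change SD of 18, 30, 40 and 60 microns. If 80% of crossings are attributed to DME, these fall to 16%, 9%, 6% and 3%. For the any-complication composite the gain was about 0-6%.

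**7. Type I error.** With 17% DME in both arms and 1,500 trials, rejection was 6.3% for CMH and 5.9% for the adjusted risk difference.

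**The case against.** Much of the case for leaving the plan alone stands.

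- **No confirmatory result changes.** SAP 7.2 says that "this family of tests will be conducted hierarchically to maintain a familywise Type I error rate of 4.98" percent. DME alone and all time-to-event endpoints are outside that family. Only the composite proportion containing DME is inside it, and the gain there is small.
- **Imbalance would be visible.** Baseline CST is tabulated by arm.
- **CST may not be on one scale.** Protocol 5.2.1 allows Spectralis or equivalent values from other instruments, so raw microns may not measure distance to the threshold equally across devices.
- **Events may be too few.** About 16 events is thin for a model with several terms. In one 250-replicate null run (about 23 events, strongly prognostic CST), the adjusted risk difference rejected 7.6% of the time against 4.8% for CMH. The Monte Carlo SE is about 1.4 points, so this is a caution rather than a finding. It is a reason to keep the CMH result.
- **The factor list is not fully visible.** The text in SAP 3.3 is redacted, so the statement that CST is not a stratum rests on SAP 7.3. Protocol 5.5 mentions SD-OCT values entered into the IRT for randomization, which should be reconciled with SAP 7.3.

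A reader might also infer more than the documents support:

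- **That the Cox estimate loses precision.** Its SE does not shrink with adjustment.
- **That crossing 320 microns is itself a DME event.** That route also needs the letter loss, and both routes need investigator attribution.
- **That the CST-change model makes the SAP inconsistent.** Adjusting a change score for its own baseline is routine and does not oblige other endpoints to follow.

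**Conclusion.** The point holds as an efficiency point. No DME analysis uses baseline CST, although the value is collected and is tied to the event by definition. The CMH, log-rank and Cox analyses remain valid under randomization, and it would be wrong to read this as bias or as a threat to the primary result.

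Under the assumed inputs, adjustment lowers the variance of the DME risk difference by about 0-21%, mostly 3-15%. It adds about 0-12 points of power to the Cox test, mostly 0-5. The gain is small when events are few, when CST change is highly variable, or when the composite is analysed.

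A peak-change SD confined to 18-30 microns with sham DME of 9-15% gives an effective-sample gain of 11-17% and 5.5-7.5 points of power for the risk difference. A reader might take that as the expected benefit, but it is the favourable end. The DME rate, treatment effect, CST distribution and CST-change SD are all assumptions; the documents give none of them.

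**What to change.** Before unmasking, amend SAP 7.3 and Table 4:

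1. **Proportion with DME.** Prespecify a risk difference standardized from a logistic model with treatment, both stratification factors and continuous baseline CST, with a robust SE. Use the last pre-dose CST on a device-equivalent scale. Report it beside the CMH result and state which is the main estimate.
2. **Time to DME.** Add a supportive Cox model with baseline CST as a covariate, labelled as a conditional hazard ratio. Keep the stratified log-rank test and the Cox model with treatment only.
3. **PDR/ASNV/DME composite.** Adjustment is optional because the gain is small.

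This needs SAP wording, a few model lines and a rule for the CST scale across devices. It needs no new data, visits or participants. The downside is a second estimate for DME and a hazard ratio that must be read as conditional on CST. It should be settled before unmasking because a covariate chosen afterwards would carry little weight.
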